GTE Lowers NFκB Activation In A TLR4-Dependent Manner. NFκB centrally regulates inflammation and is activated in livers of patients and rodents with NASH. NASH. Despite pharmacokinetic studies showing that green tea catechins have limited bioavailability, short half-lives, and rapid biotransformation through phase II xenobiotic metabolism, our studies in a high-fat (HF)-induced NASH model show that catechin-rich GTE lowers hepatic NFκB activation by decreasing IκBα phosphorylation. Consistent with our goal to translate dietary GTE as an antiinflammatory strategy, our research has focused on upstream targets by which GTE limits NFκB activation. Prominent targets to limit NFκB activation in NASH include those mediated intracellularly by reactive oxygen species (ROS) and extracellularly by signaling from TNF receptor-1 and TLR4.

Further study in Nrf2-KO mice demonstrated that GTE decreased hepatic TLR4 mRNA.¹⁷ This supported the alternative hypothesis that its antiinflammatory activities are mediated through a lowering of TLR4/NFκB signaling.¹⁷ This was corroborated in WT mice fed an HF diet prior to GTE treatment.¹⁹ We reported that GTE ameliorates NASH while lowering hepatic mRNA of TLR4, its co-receptors

CD14 and MD-2, and adapter protein MyD88.¹⁹ GTE also decreased circulating endotoxin that was otherwise increased in HF control mice.¹⁹ In our recent report,⁸ GTE in WT mice fed an HF diet inhibited NASH and hepatic NFκB activation to levels not different from those of loss-of-function TLR4 mutant mice fed an HF diet. GTE also lowered serum endotoxin independent of genotype. Thus, GTE protects against NASH consistent with a mechanism of inhibiting TLR4-mediated NFκB activation.

Hepatic TLR4 signaling is mediated through the adaptor proteins MyD88 and TRIF, which regulate "early" and "late" NFκB activation, respectively. MyD88-dependent signaling occurs immediately after cell surface binding of LPS. In contrast, TRIF-dependent signaling first requires endocytosis of LPS, which facilitates endotoxin clearance. Neither GTE nor TLR4 genotype affected TRIF, whereas GTE lowered hepatic MyD88 and circulating endotoxin regardless of genotype. This suggests that GTE attenuates NFκB activation in a TLR4/MyD88-dependent manner and lowers endotoxemia, likely without affecting LPS clearance. These findings strongly support examining GTE to target endotoxin to mitigate TLR4 inflammation.

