In conclusion, evidence shows that 1) limiting gut-derived endotoxin is an antiinflammatory strategy, 2) GTE lowers TLR4/NFκB-dependent inflammation, and 3) GTE improves gut health through improving gut barrier function and alleviating gut dysbiosis. Our team has the expertise and experience to safely perform controlled crossover interventions to assess metabolic parameters, gut barrier

permeability, and gut microbiota composition. Thus, after completing these studies we expect to substantially advance a critically needed strategy to manage disease-promoting, systemic inflammatory responses that are driven by endotoxemia.

Anticipated Results

Preclinical evidence supports the gut-level benefits of catechin-rich GTE to limit metabolic endotoxemia. ^{8,19} We expect these preclinical findings to be translated to similar gut-level improvements in MetS persons utilizing a novel, catechin-rich GTE confection (i.e. snack food). We expect to achieve >95% compliance (based on returned confections and circulating catechins) without any adverse effects or changes in body mass or energy intakes. Based on our mouse studies, ^{8,19} GTE is expected to decrease serum endotoxin in a time-dependent manner, and most substantially among MetS persons due to their endotoxemia. These benefits are expected to occur through an antiinflammatory mechanism that attenuates gut-derived endotoxin translocation. This would be consistent with GTE reducing endotoxin translocation to the portal vein by increasing intestinal expression of TJPs^{8,19} Thus, GTE will decrease small intestinal and colonic permeability, based on decreased urinary excretion of lactulose/mannitol (0-5 h) and sucralose (0-24 h), respectively. ⁴⁶

Similar to our studies, GTE also will alleviate gut dysbiosis that is known to occur in MetS persons (e.g. depleted populations of SCFA-producing bacteria⁴⁷). Selective antimicrobial activities of GTE will decrease LPS-derived Gram-negative bacteria (e.g. *Bacteroides*).^{42,44} GTE will also increase commensal bacteria, including *Clostridia* (Cluster XIV and IV) and other members of the Grampositive Phyla *Firmicutes* that generate SCFAs.^{48,49} This will be corroborated by greater fecal butyrate and other straight chain SCFAs. Thus, these findings would suggest a mechanism, at least in part, that the alleviation of gut dysbiosis restores butyrate generation.

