Plasma and Fecal Catechins and Catechin-Metabolites. Using our targeted LC-MS/MS-based panel of >50 metabolites, we will quantify GTE catechins and metabolites in fecal samples (d 27) and plasma (d 0, 14, 28) following enzymatic hydrolysis with β-glucuronidase/sulfatase. Analyte identification and quantification will be confirmed by comparing fragmentation patterns relative to purified standards or reference databases. In addition to defining the interactive effects of MetS status and GTE treatment on catechin metabolism, time-dependent plasma measures will objectively establish subject compliance to the dietary intervention.

Fecal Short Chain Fatty Acids. Separate LC-MS/MS procedures that are established based on a published report, 33 will evaluate ten C2-C6 straight chain SCFAs (i.e. butyrate, acetate, propionate) and branched chain SCFAs (e.g. isobutyric acid, isovaleric acid). Straight chain SCFAs are predominantly from bacterial fermentation of fibers whereas branched chain SCFAs are derived mainly from bacteria metabolism of branched chain amino acids. The former are often depleted with gut dysbiosis whereas the latter are often increased. In brief, fecal SCFAs are derivatized with 3-nitrophenylhydrazine to increase their stability prior to injecting on the LC-MS/MS system operated in ESI mode and quantifying against area ratios of authentic standards relative to 13C6-3NPH.

Host and Intestinal Inflammation. At wk 4, we will define the effects of GTE on inflammatory responses. We will assess intestinal inflammation by measuring fecal calprotectin and myeloperoxidase (i.e. indices of neutrophil inflammatory responses) by ELISA as we described. We will also measure systematic inflammatory responses in plasma by ELISA (CRP, IL-6 and -8, TNFα, MPO) and by RT-PCR analysis of peripheral blood mononuclear cells (PMBCs; isolated at blood collection) to assess the expression of genes involved in TLR4/NFκB signaling (TLR4, MyD88, p65, IL-6 and -8, TNFα, MPO, MCP-1).

D. Detailed Study Procedures

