Participants will be asked to consume 6 confections each day (2 with each meal) for 4 weeks. Consumption of 6 GTE-rich confections is equivalent to delivering 1 g GTE/d. At the first visit, participants will provide a fasting blood sample and then receive a 2-wk supply of confections. Halfway through the intervention (d 14), participants will visit the study center in a fasted state (10-12 h). Participants will return any leftover confections. After a 5 min stabilization period, a single fasting blood sample will be collected following procedures stated above. After collecting blood, the participants will be provided the final 2-wk supply of confections. At the conclusion of the intervention phase (d 28), participants will perform a gut permeability test and provide another fasting blood sample. Compliance will be evaluated based on the number of confections returned throughout the study as well as objectively by measuring catechin/catechin-metabolites in the plasma. To ensure randomization, a random number generator will be used to randomly assign the sequence by which the participant will complete each of the interventions.

Gut Permeability Test. On the morning of testing at d 28 of the intervention, participants will arrive at the study center after abstaining from food and only consuming water for 10-12 hours. A gut permeability test will be conducted as described⁸⁵. Upon arrival, participants will be asked to empty their urinary bladder. Subsequently, they will then be asked to ingest a drink containing 40 g sucrose, 5 g lactulose, 1 g mannitol, 1 g sucralose, and 1 g erythritol dissolved in water (250 mL). Within 2-hours after ingesting the sugar test beverage, participants will be asked to consume an additional 500 mL of water. Participants will be instructed to abstain from foods that contain artificial sweeteners during the 24-hour period. Urine will be collected from 0-5 and 6-24 hours in sterile containers with 10% thymol (inhibit bacterial growth). For each urinary collection period, participants will be provided 2-L urine collection bottles and a cooler with ice packs to store collected urine until they return their samples the next day.

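### Fasting plasma catechins with no specified last-dose time can corroborate recent intake, but cannot verify >95% compliance or isolate a MetS effect on catechin metabolism

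*Combined protocol and SAP*

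**What the plan says.** Section III.C (Plasma and Fecal Catechins and Catechin-Metabolites) measures a panel of more than 50 analytes in plasma ("d 0, 14, 28) following enzymatic hydrolysis with β-glucuronidase/sulfatase") and in feces (day 27). It then states the purpose: "In addition to defining the interactive effects of MetS status and GTE treatment on catechin metabolism, time-dependent plasma measures will objectively establish" subject compliance.

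Section III.D (Intervention Phase / Test Confections) sets the dosing: "Participants will be asked to consume 6 confections each day (2 with each meal) for 4 weeks". It also sets the sampling condition: "Halfway through the intervention (d 14), participants will visit the study center in a fasted state (10-12 h"). The Gut Permeability Test section requires the same 10-12 h fast on day 28.

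On compliance, the same part of III.D says: "Compliance will be evaluated based on the number of confections returned throughout the study as well as objectively by measuring catechin/catechin-metabolites in the plasma". Anticipated Results (II) puts a figure on it: "We expect to achieve >95% compliance (based on returned confections and circulating catechins").

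The background in section II reports pharmacokinetic studies showing that "green tea catechins have limited bioavailability, short half-lives, and rapid biotransformation through phase II xenobiotic metabolism". No half-life is given for any analyte. The text does not call for the clock time of the last confection before a draw, and it names no analyte or plasma level that would count as compliant.

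**The concern.** Confections go with meals and blood is drawn fasting, so both on-treatment samples are troughs at least 10 h after the last scheduled dose. If the analyte clears quickly, a trough reflects the day before an announced visit and little of the preceding two weeks. Placebo contains no GTE, so plasma carries no information on how much placebo was eaten.

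The same value is meant to show whether MetS status alters catechin metabolism. A lower level could come from faster clearance, poorer absorption, an earlier dinner or a skipped last dose. Days 14 and 28 sit at the same point of the dosing cycle, so two samples do not trace a concentration curve that would tell these apart.

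At stake are the compliance statement, a named secondary inference (MetS by GTE on catechin metabolism), and the planned correlations between catechins or metabolites and inflammatory markers.

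**Working it through.** The >95% is an expectation, not a calculated figure, so there is nothing to reproduce. The check asks what a fasting level can say about it.

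**Inputs from the protocol.** 6 confections a day, 2 per meal, for 28 days; fast of 10-12 h; plasma on treatment at days 14 and 28.

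**Assumptions.** Half-life *h* of 2 to 24 h. Simple first-order decline, equal doses. For the last two columns below, meals 12, 17.5 and 23 h before the draw, repeated for 14 days, with absorption and volume unchanged.

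**Compliance scale.** 6 × 28 = 168 confections per period. 160/168 = 95.2%, so >95% allows at most 8 missed. Dosing only on the day before each visit is 12/168 = 7%.

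**Formulas.**
- Share of the level from the last 24 h: 1 − 2^(−24/*h*). For *h* = 4: 1 − 2^(−6) = 0.984. This does not depend on the meal times.
- Level after a 10 h fast relative to 12 h: 2^(2/*h*). For *h* = 4: 2^0.5 = 1.41.
- Last meal's confections skipped: 1 − 2^(−12/*h*) / S, where S is the sum of 2^(−t/*h*) over all doses. For *h* = 4: 1 − 0.125/0.195 = 0.36.
- Half-life 25% longer: S at 1.25*h* divided by S at *h*. For *h* = 4: 0.331/0.195 = 1.70.

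| Assumed half-life | Share from last 24 h | 10 h vs 12 h fast | Level if last meal's dose skipped | Level if half-life 25% longer |
|---|---|---|---|---|
| 2 h | 100% | ×2.00 | 15% | ×2.48 |
| 4 h | 98% | ×1.41 | 36% | ×1.70 |
| 5 h | 96% | ×1.32 | 43% | ×1.58 |
| 6 h | 94% | ×1.26 | 48% | ×1.51 |
| 12 h | 75% | ×1.12 | 67% | ×1.35 |
| 24 h | 50% | ×1.06 | 81% | ×1.30 |

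**Compliance.** At half-lives of 2-6 h, someone at 7% of doses, all on the day before the visits, shows 94-100% of a full complier's level. Longer half-lives widen the view but not enough. At 12 h, dosing only the last 2 days before each visit (4/28 = 14% of days) gives 1 − 2^(−4) = 94% of the full level. At 24 h, dosing only the last 3 days (6/28 = 21%) gives 1 − 2^(−3) = 87.5%.

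**Metabolism.** At short half-lives, the permitted fasting window and one skipped meal-time dose move the level by amounts of the same order as a real 25% change in half-life. The model in Power Calculation and Data Analysis (III.B) has no term for time since dose, and its general allowance for covariates cannot use a time that was not collected.

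**The case against.** The strongest defence is that plasma was never meant to carry compliance alone. Returned confections give a percentage in both phases, and plasma is added because section II faults an earlier trial for relying on pill counts without a biomarker. That stands. A reader might infer that someone dosing only before visits would be counted as compliant, but the documents do not support this: that person would have about 168 − 12 = 156 confections to return, or would have to discard them, and no plasma cut-off for compliance is set.

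A reader might also infer that plasma is useless for both purposes. That goes too far. Levels compared with day 0 and with the placebo phase can show recent GTE intake, expose a treatment mix-up, and flag off-protocol tea. The panel includes microbial metabolites such as valerolactones. The remark about short half-lives concerns catechins, and nothing in the documents excludes longer persistence of the metabolites. Metabolism is also examined in feces on day 27.

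Random differences in timing mainly add noise to the MetS comparison. They bias it only if timing or adherence differs by health status, and the documents give no evidence that it does. Finally, visit forms are not part of the documents, so the supportable statement is that the protocol does not specify the last-dose time, not that it will go unrecorded.

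These points narrow the concern. They do not make a fasting trough a check on 28 days of intake, and without the times nobody can show that timing was balanced between groups.

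**Conclusion.** The concern holds in a limited form. Fasting plasma at days 14 and 28 is qualitative evidence of recent GTE intake. It cannot verify >95% compliance over 28 days, and it cannot speak to placebo intake. A MetS-healthy difference in fasting level mixes metabolism with dose timing and recent adherence. The 10-12 h window alone is worth about 2.0-, 1.4- or 1.3-fold at half-lives of 2, 4 or 5 h, which is noise in any case and bias if timing differs by MetS status.

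The sizes rest on assumed half-lives and simple first-order decline; the protocol says only that catechin half-lives are short. The problem shrinks for longer-lived analytes: at 24 h the window effect is 1.06-fold and the last day supplies 50% of the level. Serum endotoxin at day 28, the primary outcome, is not touched. The change is still worth making before sampling starts, because times not collected cannot be reliably recovered.

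**What to change.** 1. At days 14 and 28, record the clock time of the last confection and of the blood draw. Include time since last dose as a covariate in the GTE-phase plasma catechin and metabolite models and in the catechin-inflammation correlations. A skipped last dose then shows up as a longer interval. Other missed doses in the preceding day remain unmeasured, which is why item 3 is also needed.
2. Take percent compliance from returned-confection counts in both phases. Use plasma as a qualitative check of recent GTE intake and, in the placebo phase, of off-protocol tea.
3. Report the plasma MetS-by-GTE result as a time-adjusted difference in fasting concentration, read alongside the day 27 fecal data, and not by itself as a difference in catechin metabolism.

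The cost is one extra line on two visit forms, one covariate, and a weaker claim: compliance is no longer described as objectively established by plasma. Treatment, visits and blood volumes do not change.

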We will conduct a *randomized double-blind, placebo-controlled crossover trial* in metabolic syndrome (MetS) and healthy individuals. We will enroll adults with (n = 20) and age- and gender-matched healthy (n = 20) men and women (18-65 y). Participants will be block-randomized to receive GTE-rich (1 g GTE) or placebo confections and will be asked to consume the confections daily for 4 wk, while instructed to abstain from all tea varieties and follow a low-polyphenol diet. Blood will be collected at day 0, 14, and 28 for metabolic assessments and safety monitoring by assessing a serum chemistry panel [e.g. liver function (aminotransferases), renal function (creatinine, BUN), CBC, glucose, insulin, insulin resistance 19. At the same time points, blood pressure and anthropometrics will be assessed, and dietary nutrient and flavonoid intakes will be evaluated from 3-d food records using NDSR dietary analysis software and the NCC Flavonoid and Proanthocyanidin database as we described. On day 28, participants will provide a 3-d fecal sample. Following blood collection, they will complete a gut permeability test and collect urine through day 29 (described below). Upon completing these procedures, participants will undergo ~1-mo wash-out before repeating the study identically, but with crossover to the alternate treatment.

GTE-rich Confections. The [name] and [name] labs have previously developed a starch-based GTE-rich confection⁷³ as a successful catechin delivery system. For this application, we will modify this

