Power Calculation and Data Analysis. We performed a power analysis using serum endotoxin (day 28) as the primary outcome. Mean serum endotoxin of MetS and healthy adults was used to predict a conservative 30% improvement by GTE in MetS persons; this corresponds to a 10 EU/mL decrease in endotoxin in MetS. Simulations were used to estimate power based on 20 healthy and 20 MetS adults randomized to treatment vs control in a 50/50 ratio, respectively. Based on a linear model with treatment and health status, and within-subject measures, we will have >90% power (α =0.05) to detect the primary contrast of interest (GTE vs placebo in MetS adults) and additionally, >85% power (α =0.05) to detect an interaction between treatment and health status. Most data will be analyzed by linear mixed effects models (LMMs) with random effect for subjects (to account for repeated measures) and fixed effects for health status, gender, GTE treatment, time period, and their interactions. Multivariate regression analysis will define correlations between study variables with consideration of potential covariates. Statistical significance for all analyses will be set at P≤0.05.

C. Measurement/Instrumentation

Anthropometric Parameters and Blood Pressure. At screening, participants will rest for 15 minutes prior to determining blood pressure using an automated cuff. BMI will be calculated from height determined from a wall-mounted stadiometer and weight from a calibrated scale. Waist circumference will be assessed at the level of the umbilicus using a nonflexible measuring tape.

Blood Chemistries. At screening, fasting plasma glucose, triglyceride, and HDL-cholesterol will be measured by spectrophotometry utilizing validated clinical assays (Pointe Scientific). At day 0, 14, and 28 of the interventions, collected blood will be sent to The Ohio State University Medical Center for metabolic evaluations by assessing a serum chemistry panel [e.g. [e.g. liver function (aminotransferases), renal function (creatinine, BUN), CBC, glucose, insulin, insulin resistance⁷⁹].

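### The MetS-status-by-GTE test on plasma catechins does not in general hold its 5% level if the plan's subject-only random-effect model is fitted to all six samples per person

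*Combined protocol and SAP*

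**What the plan says.** Section III.C (Plasma and Fecal Catechins and Catechin-Metabolites) plans a targeted panel of more than 50 metabolites. Plasma is taken at days 0, 14 and 28 of each phase, and feces at day 27. One stated purpose is "defining the interactive effects of MetS status and GTE treatment on catechin metabolism"; another is to check compliance.

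The analysis text is in section III.B (Power Calculation and Data Analysis): "Most data will be analyzed by linear mixed effects models (LMMs) with random effect for subjects", with "fixed effects for health status, gender, GTE treatment, time period, and their interactions". It adds: "Statistical significance for all analyses will be set at P≤0.05". It gives no residual-variance structure, within-phase correlation, subject-by-treatment term or transformation. It does not say which visits enter the catechin test, or whether the time term means visit or crossover period.

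On exposure, the placebo confection contains no GTE, the wash-out lasts about a month, and participants are "instructed to abstain from all tea varieties and follow a low-polyphenol diet" (section III.A). The background section notes that "green tea catechins have limited bioavailability, short half-lives". There are 20 MetS and 20 healthy participants.

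**The concern.** Each person gives six plasma values, of which only GTE days 14 and 28 follow exposure. For a tea-specific catechin, both day-0 values and both placebo values could be low with little spread, while the two exposed values vary between people. A random-intercept model with one residual variance averages the variance over all six cells and applies it to a contrast that rests on the two variable ones. It also treats those two as no more alike than any other pair from the same person. Yet a person who absorbs or metabolises catechins unusually will tend to do so at both visits.

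Both features can make the standard error of the status-by-GTE interaction too small. The trial would then report differences in catechin metabolism between MetS and healthy adults more often than the stated threshold allows, analyte by analyte.

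**Working it through.** **Inputs from the documents.** 20 + 20 participants; six plasma samples per person, two of them after GTE; threshold 0.05 (taken as two-sided); a subject random effect only.

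**Assumed, because the documents do not give them.** SD *s* on GTE days 14 and 28, with correlation *r* between them; other cells mutually uncorrelated, with the SDs shown below; no true status effect; one residual variance.

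**The plan's own figures.** The only computed ones are the endotoxin powers (>90% and >85%). They concern another outcome and cannot be reproduced because no SD is given. The figure that matters here is the nominal 5%. In a control simulation with equal variances and a true random intercept, the six-sample test gave 4.8-5.1%, so it is valid when its own assumptions hold.

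**Near-zero background.** Let V be the sum of the six variances, here 2s². The pooled within-person variance is

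[V − (V + 2rs²)/6]/5 = s²(1/3 − r/15).

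- Day-28 GTE-minus-placebo difference: the model uses 2s²(1/3 − r/15); the true variance is s². At r = 0.5 that is 0.60s² against s². The SE ratio is √0.60 = 0.775 and the error is 2[1 − Φ(1.96 × 0.775)] = 12.9%.
- Mean of three GTE visits minus mean of three placebo visits: the model uses (2/3)s²(1/3 − r/15); the true variance is s²(2 + 2r)/9. At r = 0 both are 0.222s² and the error is 5.0%. At r = 0.5 they are 0.200s² and 0.333s², again 12.9%.

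The group comparison multiplies true and model variances by the same factor (1/20 + 1/20), so the ratios carry over to the interaction.

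| r | Day 28, formula | Day 28, simulated | Visit-averaged, formula | Visit-averaged, simulated |
|---|---|---|---|---|
| 0 | 11.0% | 11.3% | 5.0% | 5.6% |
| 0.3 | 12.1% | 11.9% | 9.6% | 9.8% |
| 0.5 | 12.9% | 13.2% | 12.9% | 13.0% |
| 0.7 | 13.8% | 14.0% | 16.3% | 16.6% |
| 0.9 | 14.7% | 15.2% | 19.8% | 20.4% |

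Simulations used 20,000 null trials per setting, with background SD 5% of the GTE-visit SD.

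**Two causes.** The day-28 test is already inflated at r = 0, so unequal variance alone is enough there. The visit-averaged test is at 5% when r = 0 and rises only with r, so there the driver is the missing subject-by-treatment term.

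**Other contrasts from the same six-sample model.** The mean of days 14 and 28 gives 11-31% over r = 0 to 1. The day 0-to-28 change gives 2.8-4.8%, which is conservative.

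**More variable background** (SDs relative to *s*; r from 0 to 0.7).

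- Day-0 SD 0.5, placebo SD 0.25: V = 2.625s². At r = 0 the pooled variance is 0.4375s², so the model uses 0.875s² against a true 1.0625s², an error of 7.5%. Simulated: 7.7-9.3% at day 28 and 5-14% visit-averaged.
- Day-0 SD 1, placebo SD 0.5: V = 4.5s². At r = 0 the model uses 1.50s² against a true 1.25s², an error of 3.2%; at r = 0.7 it is 3.8%. The visit-averaged test gives 5-9%.
- All SDs equal: 5-6% at day 28, 5-8% visit-averaged.

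**Remedies under the same null.** A per-person GTE-minus-placebo contrast compared between groups gave 4.4-5.4% in every setting. Comparing the groups on GTE-phase values only gave 4.7-5.4%, and a day-28-only model 5.2%. Separate residual variances for exposed and unexposed samples, with only a random intercept, repaired day 28 (4.4% and 5.2% at r = 0.5 and 0.7) but left the visit-averaged test at 10.9% and 13.3%. A subject-by-phase effect without separate variances left 9-10% at day 28.

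**The case against.** The strongest objection is to the near-zero background. The intervention timeline places the diet instruction after the day-0 blood draw, and no diet is stated for the wash-out, so neither day-0 sample is clearly taken on the restricted diet. On the diet, polyphenols are said to fall by only 45% from 1568 mg/d, leaving about 0.55 × 1568 = 862 mg/d. Metabolites shared with other foods may then vary without GTE. Short half-lives also cut both ways: samples are fasting, so parent catechins may be low on GTE days too. All this stands. It is why the size is conditional, and why near-zero background is most plausible only for tea-specific parent catechins.

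Secondly, a reader might infer that the plan prescribes one residual variance for catechins and that the error is therefore 12-16%. The documents do not support that. The model is assigned to most of the data without naming catechins, a single variance is a software default rather than a statement, and no visits are specified. A day-28-only analysis would hold 5%.

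A reader might also blame unequal variance alone. That fits the day-28 contrast but not the visit-averaged one.

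Finally, fecal catechins (one sampling day per phase) and the primary endotoxin test are not touched. The objections limit the size and scope. They do not make the six-sample random-intercept test valid in general.

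**Conclusion.** The point holds in conditional form. If the only model described is fitted to all six plasma samples with its default residual structure, the status-by-GTE test does not in general have a 5% error rate. With near-zero background the error is about 11-15% at day 28 and about 5-20% averaged over visits, for correlations from 0 to 0.9. With substantially variable day-0 or placebo values it is smaller, and at day 28 it may fall to about 3-4%. These figures rest on assumed SDs and correlations that the documents do not supply. The outcome is secondary, but the interaction is a stated purpose of the measurement. It would be tested across a panel of more than 50 metabolites at an unadjusted 0.05, so the method should be fixed in advance.

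**What to change.** In both the data-analysis paragraph of section III.B and the catechin paragraph of section III.C, state how the status-by-GTE effect on plasma catechins and metabolites is tested. Form one GTE-minus-placebo contrast per person at post-dose visits (day 28, or the mean of days 14 and 28; choose one in advance) and compare it between MetS and healthy participants. For analytes essentially absent without GTE, GTE-phase day-14 and day-28 values alone may be compared; name those analytes beforehand, because this version no longer subtracts background differences between the groups.

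If a joint model is kept, give it a random subject-by-treatment effect as well as separate residual variances for exposed and unexposed samples. Separate variances alone are not enough.

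The cost is analysis wording; no new data are needed. Error degrees of freedom fall to 40 − 2 = 38, against 38 × 5 = 190 within-person in a six-sample model without gender. The critical *t* rises from 1.97 to 2.02, so P values are slightly larger for that reason, apart from the change due to correcting the standard error.
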